5.4.1.2.3. Supplementary Estimands

The supplementary estimands defined in Section 5.3.1.2.2.1 (Hypothetical Strategy) and Section 5.3.1.2.2.2 (Treatment Policy Strategy) for the primary endpoint will also be used for selected binary secondary endpoints:

- Proportion of participants achieving PASI 90 ($\geq 90\%$ improvement from baseline in PASI) at Week 16
- Proportion of participants achieving PASI 100 (100% improvement from baseline in PASI) at Week 16
- Proportion of participants achieving an IGA score of cleared (0) or minimal (1) at Week 16
- Proportion of participants achieving an IGA score of cleared (0) at Week 16

The following table provides the list of variables, summary measure (population-level summary) and intercurrent event strategy for secondary endpoints.

Secondary Endpoint	Variable	Summary Measure (Population-level summary)	Intercurrent Event Strategy
1	Binary response variable, where a responder is defined as a participant achieving a PASI 90 response at Week 16	Difference in the proportions of participants achieving a PASI 90 response at Week 16 between JNJ-77242113 treatment groups and placebo group.	Same analysis strategies as the primary estimand as specified in section 5.3.1.2.1 and two supplementary estimands specified in section 5.3.1.2.2.
2	Binary response variable, where a responder is defined as a participant achieving a PASI 100 response at Week 16	Difference in the proportions of participants achieving a PASI 100 response at Week 16 between JNJ-77242113 treatment groups and placebo group.	Same analysis strategies as the primary estimand as specified in section 5.3.1.2.1 and two supplementary estimands specified in section 5.3.1.2.2.
3	Binary response variable, where a responder is defined as a participant achieving an IGA scores of cleared (0) or minimal (1) at Week 16	Difference in the proportions of participants achieving an IGA score of cleared (0) or minimal (1) at Week 16 between JNJ-77242113 treatment groups and placebo group.	Same analysis strategies as the primary estimand as specified in section 5.3.1.2.1 and two supplementary estimands specified in section 5.3.1.2.2.

4	Binary response variable, where a responder is defined as a participant achieving an IGA scores of cleared (0) at Week 16	Difference in the proportions of participants achieving an IGA score of cleared (0) at Week 16 between JNJ-77242113 treatment groups and placebo group.	Same analysis strategies as the primary estimand as specified in section 5.3.1.2.1 and two supplementary estimands specified in section 5.3.1.2.2.
5	Continuous variable, change from baseline in PASI score at Week 16 (change = Week 16 - baseline)	LSMean difference in change from baseline in PASI at Week 16 between JNJ-77242113 treatment groups and the placebo group.	Same analysis strategies as the primary estimand specified in section 5.4.1.2.2
6	Continuous variable, change from baseline in BSA at Week 16 (change = Week 16 - baseline)	LSMean difference in change from baseline at Week 16 between JNJ-77242113 treatment groups and placebo group.	Same analysis strategies as the primary estimand specified in section 5.4.1.2.2
7	Continuous variable, change from baseline in PSSD symptoms score at Week 16 (change = Week 16 - baseline)	LSMean difference in change from baseline at Week 16 between JNJ-77242113 treatment groups and placebo group.	Same analysis strategies as the primary estimand specified in section 5.4.1.2.2
8	Continuous variable, change from baseline in PSSD sign at Week 16 (change = Week 16 - baseline)	LSMean difference in change from baseline at Week 16 between JNJ-77242113 treatment groups and placebo group.	Same analysis strategies as the primary estimand specified in section 5.4.1.2.2
9	Binary response variable, where a responder is defined as a participant with baseline symptom score ≥ 1 and achieving PSSD symptom score =0 at Week 16	Difference in the proportions of participants achieving efficacy responses at Week 16 between JNJ-77242113 treatment groups and placebo group.	Same analysis strategies as the primary estimand specified in section 5.3.1.2.1.
10	Binary response variable, where a responder is defined as a participant with baseline sign score ≥ 1 and achieving a PSSD signs score of 0 at Week 16	Difference in the proportions of participants achieving a PSSD signs score of 0 at Week 16 between JNJ-77242113	Same analysis strategies as the primary estimand specified in section 5.3.1.2.1.

		treatment groups and placebo group.	
11	Binary response variable, where a responder is defined as a participant with baseline DLQI score > 1 and achieving a DLQI score of 0 or 1 at Week 16	Difference in the proportions of participants achieving a DLQI score of 0 or 1 at Week 16 between JNJ-77242113 treatment groups and placebo group.	Same analysis strategies as the primary estimand specified in section 5.3.1.2.1.
12	Continuous variable, change from baseline in domain scores of the Patient-Reported Outcomes Measurement Information System (PROMIS-29) symptom at Week 16 (change = Week 16 - baseline)	LSMean difference in change from baseline at Week 16 between JNJ-77242113 treatment groups and placebo group.	Same analysis strategies as the primary estimand specified in section 5.4.1.2.2
13	Binary response variable, where a responder is defined as a participant achieving at least a 5-point improvement from baseline in each PROMIS-29 domain at Week 16	Difference in the proportions of participants achieving at least a 5-point improvement from baseline in each PROMIS-29 domain at Week 16 between JNJ-77242113 treatment groups and placebo group.	Same analysis strategies as the primary estimand specified in section 5.3.1.2.1.

5.4.1.3. Analysis Methods

The secondary efficacy analysis of data for study 77242113PSO2001 will be based on the FAS defined in Section 4.1. The endpoints will be summarized by intervention group. Simple descriptive statistics, such as n, mean, SD, median, IQ range, minimum and maximum for continuous variables and counts and percentages for discrete variables will be used to summarize most data. All statistical testing will be performed at a 2-sided 0.05 significance level. Nominal p-values will be presented. No adjustments for multiple comparisons will be made for the secondary endpoints.

5.4.1.3.1. Binary Endpoints

The binary secondary endpoints at Week 16 will be analyzed using the estimands described in section 5.4.1.2.2. The analysis strategy for ICEs and missing data will be handled in the same manner as the primary estimand for the primary analysis (Section 5.3.1.2.3). The proportions of participants for the above secondary efficacy endpoints will be summarized for each intervention group.

The Cochran-Mantel-Haenszel chi-square statistic stratified by baseline weight category (≤ 90 kg, > 90 kg) at a 2-sided significance level of 0.05 will be used. Difference in response rates between

each of the active and placebo groups at Week 16 adjusted for baseline weight category (≤ 90 kg, > 90 kg) using Mantel-Haenszel weight and the corresponding 95% CI will be presented.

In case of rare events, the Fisher's Exact test will be used for treatment comparisons in binary response endpoints. The proportion differences between JNJ-77242113 groups and placebo and the exact confidence intervals will be provided.

5.4.1.3.1.1. Analysis for Supplementary Estimands

Similar to the primary analysis of pair comparison, the analyses specified in Section 5.3.1.2.5.1 (Hypothetical Estimand) and Section 5.3.1.2.5.2 (Treatment Policy Estimand) for supplementary estimands will be applied to the following secondary endpoints:

- Proportion of participants achieving PASI 90 ($\geq 90\%$ improvement from baseline in PASI) at Week 16
- Proportion of participants achieving PASI 100 (100% improvement from baseline in PASI) at Week 16
- Proportion of participants achieving an IGA score of cleared (0) or minimal (1) at Week 16
- Proportion of participants achieving an IGA score of cleared (0) at Week 16

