5.4.1.2. Secondary Endpoint(s)

The secondary objectives are: (a) To characterize additional efficacy of JNJ-77242113 versus placebo, (b) To evaluate the effect of JNJ-77242113 treatment on patient-reported psoriasis severity versus placebo and (c) To evaluate the effect of JNJ-77242113 treatment on dermatology-specific and general health-related quality of life versus placebo in participants with moderate-to-severe plaque psoriasis.

The secondary endpoints to address these objectives are the following:

To characterize additional efficacy of JNJ-77242113 versus placebo

1. Proportion of participants achieving PASI 90 ($\geq 90\%$ improvement from baseline in PASI) at Week 16
2. Proportion of participants achieving PASI 100 (100% improvement from baseline in PASI) at Week 16
3. Proportion of participants achieving an IGA score of cleared (0) or minimal (1) at Week 16
4. Proportion of participants achieving an IGA score of cleared (0) at Week 16
5. Change from baseline in PASI total score at Week 16
6. Change from baseline in BSA at Week 16

To evaluate the effect of JNJ-77242113 treatment on patient-reported psoriasis severity versus placebo

7. Change from baseline in Psoriasis Symptoms and Signs Diary (PSSD) symptoms score at Week 16

8. Change from baseline in PSSD signs score at Week 16
9. Proportion of participants achieving PSSD symptoms score=0 at Week 16 among participants with a baseline symptoms score ≥ 1 .
10. Proportion of participants achieving PSSD signs score=0 at Week 16 among participants with a baseline signs score ≥ 1 .

To evaluate the effect of JNJ-77242113 treatment on dermatology-specific and general health-related quality of life versus placebo

11. Proportion of participants achieving a DLQI of 0 or 1 at Week 16 among participants with baseline DLQI score > 1
12. Change from baseline in domain scores of the Patient-Reported Outcomes Measurement Information System (PROMIS-29) at Week 16
13. Proportion of participants who achieve at least a 5-point improvement from baseline in each PROMIS-29 domain at Week 16

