5.4.1.3.2. Continuous Endpoints

Unless otherwise specified, the analyses for continuous secondary endpoints at Week 16 will be based on the following strategies to handle ICEs and missing data.

- ICEs in categories 1 - 2 in the primary estimand (definitions in Section 5.3.1.2.1) will be handled with the Composite Strategy. Participants experiencing ICEs 1-2 will have a zero change (or zero improvement) from baseline assigned from that point onward.
- ICEs in categories 3 in the primary estimand (definitions in Section 5.3.1.2.1) will be handled by the Treatment Policy strategy. The analysis will be performed using observed data regardless of intercurrent events. For participants experiencing multiple ICEs, an ICE in categories 2 of the primary estimand will override an ICE in category 3.
- Missing data will not be imputed after applying the rules for intercurrent events.

To account for the missing data for continuous endpoints of change (or percent change) from baseline measured at more than one post-baseline visit, a MMRM will be used. In MMRM, missing data will not be imputed, but rather missing data will be accounted for through correlation of repeated measures in the model.

Treatment comparisons for the secondary continuous endpoints at Week 16 will also be performed using a Mixed-Effect Model Repeated Measure (MMRM) model under the assumption of missing at random (MAR) with intervention group, visit, baseline weight category (≤ 90 kg, > 90 kg), baseline value for the efficacy endpoint, treatment by visit, baseline weight category by visit and baseline value by visit interaction as explanatory factors, if appropriate. An unrestricted (UN)

variance-covariance matrix for repeated measures within a participant will be used. If the model with unstructured covariance structure does not converge, alternative covariance structures will be tried in the following order, with the first structure that converges being used in the analysis: heterogeneous Toeplitz, standard Toeplitz, and autoregressive of order 1.

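### The comparisons of PSSD symptoms = 0, PSSD signs = 0 and DLQI 0 or 1 leave the collected baseline score unused; a supportive baseline-adjusted difference would add some precision

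*SAP*

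**What the plan says.** SAP 5.4.1.2 lists three secondary endpoints with an absolute target:

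- No. 9: "Proportion of participants achieving PSSD symptoms score=0 at Week 16 among participants with a baseline symptoms score" of at least 1.
- No. 10: "Proportion of participants achieving PSSD signs score=0 at Week 16 among participants with a baseline signs score" of at least 1.
- No. 11: "Proportion of participants achieving a DLQI of 0 or 1 at Week 16 among participants with baseline DLQI score" above 1.

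SAP 5.4.1.3.1 tests all binary secondary endpoints with "The Cochran-Mantel-Haenszel chi-square statistic stratified by baseline weight category", "at a 2-sided significance level of 0.05 will be used". It reports the difference between "each of the active and placebo groups at Week 16 adjusted for baseline weight category" with Mantel-Haenszel weights. For rare events it switches to Fisher's exact test and exact confidence intervals.

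For continuous endpoints, the MMRM in SAP 5.4.1.3.2 includes "baseline value for the efficacy endpoint" and its interaction with visit. This covers change in PSSD symptoms and signs (secondary endpoints 7 and 8). Change in DLQI at Week 16 is exploratory (SAP 5.5.1.2.7) and reaches the same model through SAP 5.5.1.2.1.

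Randomization balances study site and weight category (Protocol 6.3). The secondary p-values are nominal (SAP 5.4.1.1).

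**The concern.** A participant who starts near zero has less far to go to reach zero than one who starts high, so the baseline score is a natural predictor of success on these three endpoints. The plan uses it only as an entry filter, and that filter removes little. A single PSSD symptom item scored 1, with the other four at 0, gives (1/5) x 10 = 2, which already passes the cut of 1. With whole-number answers, the PSSD filter therefore excludes only those who start at 0. The DLQI filter leaves scores of 2 to 30 eligible.

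No other planned analysis brings the baseline score into these comparisons. The supplementary estimands cover PASI 90, PASI 100 and the IGA endpoints. The baseline DLQI subgroups in SAP 5.7.5 are applied to PASI 75 and IGA 0/1. At stake is some precision with 40 or fewer participants per arm, and the readability of a comparison in which the arms happen to start at different severity.

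**Working it through.** **The plan's own power figure.** The only pairwise power stated is for PASI 75: at least 90% for a 35-point difference at 40 per arm (SAP 3.1). For 10% vs 45%, the pooled rate is 0.275.

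- Null SE = sqrt(2 x 0.275 x 0.725 / 40) = 0.0998; times 1.96 = 0.1957.
- Alternative SE = sqrt(0.10 x 0.90/40 + 0.45 x 0.55/40) = 0.0919.
- z = (0.35 - 0.1957) / 0.0919 = 1.68, so power is 95.4%.

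For 5% vs 40% it is 97.6%. The stated bound holds. No power is stated for DLQI 0 or 1 or for PSSD = 0, so nothing below contradicts a figure in the plan.

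**Chance imbalance.** In SD units, the difference in mean baseline between two arms of 40 has standard deviation sqrt(2/40) = 0.224. The probability that it exceeds 0.3 SD in either direction is 2 x [1 - Phi(0.3/0.224)] = 18% for one comparison. By simulation it is about 53% for at least one of the five.

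**Its effect.** Assume a log odds ratio of -0.5 or -1.0 per SD of baseline. A baseline 0.3 SD higher lowers an arm's response rate by 1.2 or 2.2 points from 10%, and by 3.2 or 5.5 points from 35%. The standard error of the difference is sqrt(0.10 x 0.90/40 + 0.35 x 0.65/40) = 0.089, about 9 points.

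**Validity of the planned test.** Under no difference at 10% or 20% in both arms, with 36 or 40 per arm, the weight-stratified CMH test rejected in 4.5 to 5.5% of simulated trials. Under a true difference, the mean estimate stayed within 0.2 points of the truth.

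**The adjusted estimate.** Fit logit P(response) = a + b(treatment) + c(weight category) + d(baseline score) in one active-placebo pair. Predict each participant's response under active and under placebo, and average the difference over the pair. Simulation: 3,000 two-arm trials per setting, 40 per arm.

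*Rejection under the null.* A plain robust SE rejected in 5.4 to 9.3% of trials, against 3.9 to 5.9% for CMH. With an HC3-type SE, in which each residual is divided by one minus its leverage, the rate was 3.4 to 5.8%.

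*Power with the corrected SE:*

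| Baseline OR per SD (assumed) | True rates (assumed) | CMH | Adjusted | Gain (points) |
|---|---|---|---|---|
| 2 | 10% vs 40% | 89.7% | 90.5% | 0.8 |
| 2 | 20% vs 50% | 79.8% | 81.8% | 2.0 |
| 3 | 10% vs 40% | 89.7% | 93.0% | 3.3 |
| 3 | 20% vs 50% | 80.6% | 86.1% | 5.5 |

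Repeat runs put the gain at 0 to 4 points for an odds ratio of 2 and at 2 to 7 points for 3. Relative efficiency rose by about 6 to 9% and 16 to 20%; the lowest values in any run were 5% and 13%. At an odds ratio of 1, about 1 power point was lost. At 5% in both arms, relative efficiency was 0.86 to 0.95, so adjustment did harm there.

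**The case against.** The strongest case is that nothing is wrong. Stratifying on weight matches the non-site randomization factor and the pairwise PASI 75 analysis. The test keeps its error rate, and the confidence interval already allows for chance imbalance. The p-values are nominal, and the trial's success rests on the PASI 75 dose-response signal (Protocol 9.4.2.1.1.1). No baseline distribution or association is given; DLQI 2 to 30 and PSSD up to 100 are scale limits, not observed spread. All of this stands, and it is why the point is an improvement only.

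A second objection also stands: replacing CMH by standardization with an ordinary robust SE would be worse than the plan, because it rejects too often at this sample size. Using a penalised fit in place of the Fisher rule would give up exact inference where adjustment does not help.

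A reader might infer that the SAP contradicts itself by adjusting for baseline in one model and not in the other. It does not: these are different endpoints and different methods, and for DLQI the MMRM is exploratory only. A reader might also extend the point to every fixed target. For IGA, entry requires a score of at least 3 on a 0 to 4 scale, which leaves two baseline levels, and adjustment gave no gain. PASI 100 has the same form but was not examined here.

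What the objections do not remove is that a collected and probably informative covariate is unused in these three comparisons.

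**Conclusion.** The point holds as unused precision. A reader might conclude that the planned comparisons are biased, or that imbalance passes uncorrected into the results; neither is supported. A 0.3 SD imbalance would shift an arm's rate by roughly 1 to 5 points against a standard error of about 9, and the interval already reflects that variation.

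The gain is small at an odds ratio of 2 per SD and moderate at 3. It rests on those assumed odds ratios, on a normally distributed baseline, on 45% of participants in the heavier stratum, and on response rates of 10% vs 40% or 20% vs 50%. It is absent when responders are few, which is plausible for PSSD = 0 on placebo. No primary conclusion depends on it.

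**What to change.** Add to SAP 5.4.1.3.1, for endpoints 9 to 11 only, a pre-specified supportive estimate of the risk difference:

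- logistic regression on treatment, weight category and the continuous baseline score of the same instrument;
- standardized over the participants in each active-placebo pair;
- 95% confidence interval from a leverage-corrected (HC3-type) robust SE.

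Keep the weight-stratified CMH p-value. Keep Fisher's exact test and the exact interval when events are rare, and do not substitute a penalised fit there. The SAP does not say what counts as rare; state it, so that it is fixed in advance when the adjusted estimate is left out.

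The cost is one SAP paragraph and a little programming, with no change to data collection or conduct. The statistical cost is about 1 power point on the adjusted analysis if baseline is not prognostic.

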5.4.1.3.2. Continuous Endpoints

Unless otherwise specified, the analyses for continuous secondary endpoints at Week 16 will be based on the following strategies to handle ICEs and missing data.

- ICEs in categories 1 - 2 in the primary estimand (definitions in Section 5.3.1.2.1) will be handled with the Composite Strategy. Participants experiencing ICEs 1-2 will have a zero change (or zero improvement) from baseline assigned from that point onward.
- ICEs in categories 3 in the primary estimand (definitions in Section 5.3.1.2.1) will be handled by the Treatment Policy strategy. The analysis will be performed using observed data regardless of intercurrent events. For participants experiencing multiple ICEs, an ICE in categories 2 of the primary estimand will override an ICE in category 3.
- Missing data will not be imputed after applying the rules for intercurrent events.

To account for the missing data for continuous endpoints of change (or percent change) from baseline measured at more than one post-baseline visit, a MMRM will be used. In MMRM, missing data will not be imputed, but rather missing data will be accounted for through correlation of repeated measures in the model.

Treatment comparisons for the secondary continuous endpoints at Week 16 will also be performed using a Mixed-Effect Model Repeated Measure (MMRM) model under the assumption of missing at random (MAR) with intervention group, visit, baseline weight category (≤ 90 kg, > 90 kg), baseline value for the efficacy endpoint, treatment by visit, baseline weight category by visit and baseline value by visit interaction as explanatory factors, if appropriate. An unrestricted (UN)

variance-covariance matrix for repeated measures within a participant will be used. If the model with unstructured covariance structure does not converge, alternative covariance structures will be tried in the following order, with the first structure that converges being used in the analysis: heterogeneous Toeplitz, standard Toeplitz, and autoregressive of order 1.

5.4.2. Study 77242113PSO2002

5.4.2.1. Multiplicity Adjustment for Testing Procedures

Similar to the primary endpoint analysis of study 77242113PSO2002, since there is no reference arm (placebo), no statistical comparisons will be performed for the secondary endpoints.

5.4.2.2. Secondary Endpoints

The secondary objectives of this study are: (a) To evaluate long-term clinical response of JNJ-77242113 treatment and (b) To evaluate the effect of JNJ-77242113 treatment on patient-reported psoriasis severity in participants with moderate-to-severe plaque psoriasis.

The secondary endpoints to address these objectives are the following:

To evaluate long-term clinical response of JNJ 77242113 treatment

1. Proportion of participants achieving PASI 90 ($\geq 90\%$ improvement in PASI from baseline of the originating study) at Week 36
2. Proportion of participants achieving PASI 100 (100% improvement in PASI from baseline of the originating study) at Week 36
3. Proportion of participants achieving an IGA score of cleared (0) or minimal (1) at Week 36
4. Change from baseline of the originating study in PASI total score at Week 36

To evaluate the effect of JNJ-77242113 treatment on patient-reported psoriasis severity

5. Change from baseline of the originating study in PSSD symptoms score at Week 36
6. Change from baseline of originating study in PSSD signs score at Week 36
7. Proportion of participants achieving a PSSD symptoms score of 0 at Week 36 among participants with a baseline (in the originating study) symptoms score ≥ 1
8. Proportion of participants achieving a PSSD signs score of 0 at Week 36 among participants with a baseline (in the originating study) signs score ≥ 1

